4.2 Treatment Regimen

Prior to the day of treatment, each patient will receive an orientation to the hyperbaric chambers located in the hyperbaric medicine department within radiation oncology. A “test drive” will be performed with the patient in the chamber with air rather than 100% oxygen. This will verify the patient’s ability to equalize pressure in the middle ear and will assure that he or she is not claustrophobic. A small percentage of patients (estimated at 15%, based on prior experience) may be unable to achieve pressure equalization in the middle ear. These patients will be offered placement of a tympanostomy tube to facilitate HBO treatment and to enable continuation with the protocol, a simple procedure performed typically by a Physician’s Assistant in DHMC’s Section of Otolaryngology.

On the day of SRS, during HBO treatment the patient will receive oxygen under pressure while lying supine inside the hyperbaric chamber. HBO will be given at 2.4 ATA. Compression will occur at 3.77 feet/minute. The patient will stay at depth for 30 minutes. Decompression will be performed over a 5-minute time span.

Patients then will be transported from the HBO chamber via stretcher to the SRS treatment area while receiving 100% oxygen via non-rebreather face mask @15L/minute to help maintain oxygen saturation.

Patients then will receive radiosurgery for their metastases as detailed below (Section 5.3 – “SRS Treatment Visit”).

A stopwatch will be used to document the time elapsed from when the patient exits the hyperbaric chamber to when he/she starts receiving SRS (“beam-on”). The goal of this time interval should be kept at ≤ 15 minutes. Elapsed time from leaving the hyperbaric chamber to completion of SRS will be recorded as well.

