7.3 Reporting of Serious Adverse Events and Unanticipated Problems

Adverse events that will be reported are those that are:

- At least possibly related to study participation,
- unexpected, and
- serious or involve risks to subjects or others
(see definitions, section 7.1).

The following information will be included in the adverse event report initial report:

- Study identifier
- Subject number
- A description of the event
- Date of onset
- Current status
- Whether study treatment was discontinued

- The reason why the event is classified as serious
- Investigator assessment of the association between the event and study treatment

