7.4 Stopping Rules

An internal stopping rule is set in place whereby the study will be terminated if (1) feasibility appears unattainable, or (2) a significant number of patients experience a significant adverse event (SAE) as outlined above:

- Regarding the primary endpoint of feasibility, we anticipate a steep learning curve for treatment of patients on this trial. The overall goal is to begin SRS within 15 minutes of exiting the HBO chamber; however, it is known that oxygen levels remain elevated in the brain up to 30 minutes after HBO treatment. The following stopping rules will be applied:
 - Analysis after enrollment of first 10 patients demonstrates no more than two patients (20%) treated within 30 minutes of HBO chamber exit.
 - Analysis after enrollment of first 15 evaluable patients demonstrates no more than five patients (33%) treated within 30 minutes of HBO chamber exit.
- Regarding the secondary endpoint of noninferiority, every patient who receives treatment on this protocol will be evaluated at every patient encounter for adverse events. Toxicities will be graded using the Common Toxicity Criteria Adverse Events (CTCAE) v4.0 of the National Cancer Institute.
 - Overall incidence of adverse events in this study will be reviewed every three months.
 - At time of any such review, if more than 40% of enrolled patients (minimum of 5 patients) experience SAEs that are deemed likely related to the protocol treatment (HBO combined with SRS), then the study will be terminated (i.e. more than 2 out of 5 patients, or more than 4 out of 10 patients, for example).
 - Note that some SAEs are expected in this patient population, given the nature of the disease process that is being treated. The stopping rule of 40% was elected as representing an incidence level significantly higher than that expected routinely in this patient population.
- It is the responsibility of the Principal Investigator to oversee the safety of the study. This safety monitoring will include careful assessment and appropriate reporting of adverse events as noted above, as well as quarterly review by the Norris Cotton Cancer Center Data and Safety Monitoring and Accrual Committee (see section 9 Auditing, Monitoring and Inspecting). Medical monitoring will include a regular assessment of the number and type of serious adverse events.

8 Data Handling and Record Keeping

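### The 40% safety stopping rule counts treatment-related SAEs against enrolled rather than treated patients, and explains its limit by disease-process SAEs that the count leaves out

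*Combined protocol and SAP*

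**What the plan says.** Section 7.4 (Stopping Rules) ends the study "if more than 40% of enrolled patients (minimum of 5 patients) experience SAEs that are deemed likely related to the protocol treatment", which it identifies as HBO combined with SRS. Its illustrations are "more than 2 out of 5 patients, or more than 4 out of 10 patients, for example". The timing is given as "Overall incidence of adverse events in this study will be reviewed every three months".

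The same bullet defines who is assessed: "every patient who receives treatment on this protocol will be evaluated at every patient encounter for adverse events".

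The limit is explained in two sentences: "Note that some SAEs are expected in this patient population, given the nature of the disease process that is being treated", and then "The stopping rule of 40% was elected as representing an incidence level significantly higher than that expected routinely in this patient population". Neither gives a rate or a source.

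Other sections fix the order of events. Consent is completed at Visit 1 (Section 5.1), the HBO consult and practice dive are at Visit 2 (5.2), and HBO and SRS are given at Visit 3 (5.3). A patient withdrawn within a year of enrollment does not count towards the 20 evaluable patients and is replaced (3.4.3).

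**The concern.** There are two separate problems.

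- **Denominator.** Someone who has consented but not yet been treated, or who withdraws before HBO, cannot have an SAE related to HBO combined with SRS. Counting that person as enrolled can only leave the number of events needed to stop unchanged, or raise it. The rule as worded is therefore never stricter than one based on treated patients, and sometimes it is looser.
- **Rationale.** The limit is defended by reference to SAEs that the disease itself is expected to produce. The count admits only SAEs judged likely related to treatment, so the events that explain the limit are not the events compared with it.

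This is the only numerical safety stop in a study of a combination that Section 1.1 says has not been studied before. At stake is whether a reader of the 40% knows what true rate among treated patients would end the study, and with what probability.

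**Working it through.** **Inputs from the documents.** Limit: more than 40%. Minimum: 5 patients. Target: 20 evaluable patients. Accrual: 20 patients in 36 months (6.1).

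**Assumptions.** The number of untreated enrolled patients, *u*, is not in the documents and is varied from 0 to 3. True related-SAE rates of 20% to 50% are illustrative.

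**1. The plan's own examples.** With *n* patients in the denominator, the rule stops at k = floor(0.40 × n) + 1 patients with a related SAE. For n = 5, k = 3; for n = 10, k = 5. Both match the stated examples. For n = 15 and n = 20, k = 7 and 9.

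**2. Effect on the trigger.** With *m* treated, n = m + u. Patients with related SAEs needed to stop:

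| Treated | u = 0 | u = 1 | u = 2 | u = 3 |
|---|---|---|---|---|
| 5 | 3 | 3 | 3 | 4 |
| 8 | 4 | 4 | 5 | 5 |
| 10 | 5 | 5 | 5 | 6 |
| 15 | 7 | 7 | 7 | 8 |
| 20 | 9 | 9 | 9 | 10 |

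One or two untreated patients change nothing at exactly 5, 10, 15 or 20 treated, but can matter in between. With 8 treated and 2 untreated, the trigger moves from 4 to 5. At a true rate of 50%, the single-look chance of stopping then falls from 0.637 to 0.363.

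An example with u = 3: 5 treated, 8 enrolled, 3 related SAEs. Among treated patients this is 3/5 = 60%. Against enrolled patients it is 3/8 = 37.5%, so the study does not stop.

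**3. Chance of ever stopping.** Exact binomial recursion: add one treated patient at a time, with related-SAE probability *p*. At each m from 5 to 20, remove as stopped every path whose count exceeds 0.40 × (m + u).

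| u | p = 20% | p = 30% | p = 40% | p = 50% |
|---|---|---|---|---|
| 0 | 18.0% | 45.9% | 74.6% | 92.3% |
| 1 | 12.9% | 37.2% | 67.0% | 88.8% |
| 2 | 8.5% | 29.0% | 59.4% | 85.0% |
| 3 | 3.6% | 18.0% | 46.5% | 76.6% |

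With looks only at 5, 10, 15 and 20 treated, the figures for p = 30/40/50% are 27.6/57.9/84.3% for u = 0, 1 or 2, and 9.9/33.5/66.4% for u = 3. Quarterly reviews will not generally fall at those sizes.

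**4. The minimum of 5.** As written, this too is counted in enrolled patients. With 5 enrolled, 3 treated and 3 related SAEs, 3/5 = 60% and the rule stops already. Starting the recursion at 5 enrolled instead of 5 treated changes the u = 3 row to 20.4/48.6/77.7% for p = 30/40/50% and leaves u = 1 and u = 2 unchanged.

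**5. Rationale against count.** Suppose background SAEs occur in a proportion *b* of patients, independently of related SAEs (assumed b = 10%, 20%, 30%). Any-cause incidence is 1 − (1 − b)(1 − r), where *r* is the related rate.

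- At r = 40%, any-cause incidence is 46%, 52% or 58%.
- Any-cause incidence equals 40% at r = 1 − 0.60/(1 − b), which is 33%, 25% or 14%.

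A limit of 40% therefore means something quite different for related SAEs than for all SAEs. This does not depend on u.

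**The case against.** The strongest reply is that *enrolled* is loose wording. Section 3.3 sends a patient who wishes to enroll on to hyperbaric screening, so enrollment might follow that screen. The worked examples say only patients, and the feasibility rule in 7.4 ties its first look to enrollment when it means treated patients. This may well be what was intended. But the rule says enrolled, no section defines the term, and 7.4 uses *evaluable* for the 15-patient look, so the words are not plainly interchangeable.

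The number untreated may also be small. Accrual of 20/36 ≈ 0.56 per month, with Visit 1 bloodwork due within 30 days of SRS, implies about 0.6 patients waiting at a time. Two or three untreated patients would need withdrawals before treatment, for which the documents give no rate. That stands, and it is why the results are shown as a range starting at zero. The model also holds u fixed from the fifth treated patient onward; u = 3 at that point is 3 of 8 enrolled.

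A reader might infer u = 3 from Section 4.2: "A small percentage of patients (estimated at 15%, based on prior experience) may be unable to achieve pressure equalization in the middle ear", and 15% of 20 is 3. The documents do not support this. Those patients are offered a tympanostomy tube so that they can continue, so 15% is not a dropout rate.

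A reader might also see a contradiction with Section 7.3, whose threshold is "At least possibly related to study participation". That section governs reporting, whereas 7.4 governs termination. A wider net for reporting than for stopping is ordinary.

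On the rationale, the note about disease SAEs can partly be read as explaining why only related events count, and protocol treatment includes SRS, so some treatment-related SAEs may be routine. Even on that reading, no expected related-SAE rate is given to support 40%.

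Finally, the data and safety monitoring committee reviews the study quarterly and can suspend or terminate it (9.1). That is a real backstop, but it has no numerical criterion of its own.

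**Conclusion.** The point holds in two limited parts.

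First, the denominator as written can include patients who cannot have the event, and the effect runs only towards later stopping once 5 are treated. Its size depends on a number that the documents do not give. With none untreated it is nil. With 1 to 3 untreated and a check after each treated patient, the chance of stopping at a true 40% related rate drops from 74.6% to between 67.0% and 46.5%. With 1 or 2 untreated and looks only at 5, 10, 15 and 20 treated, nothing changes.

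Second, the rationale for 40% refers to events that the count excludes, and no related-SAE benchmark or stopping probability is stated. This is the firmer part, because it does not depend on the number untreated, although the text allows a partly benign reading.

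A reader might go further and conclude that the study would run on unsafely, or that 40% is the wrong limit. The documents support neither: the committee can act without the rule, and there is no expected related-SAE rate against which to judge the limit.

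**What to change.** In Section 7.4:

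1. Make the denominator patients who have started HBO.
2. Say whether the minimum of 5 counts treated or enrolled patients.
3. Reconcile the rationale with the events counted. Either count all SAEs and justify the limit from an all-cause background rate, or keep the related-only count and justify the limit from an expected related-SAE rate. State the rate used and its source.
4. State the rule's stopping probabilities over a range of true rates at the planned review schedule.

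No limit is proposed here; that is for the investigators and the monitoring committee.

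The cost is a wording change and a short calculation, with two trade-offs. If the minimum counts treated patients, the rule cannot act before 5 are treated, whereas now it can act once 5 are enrolled. Otherwise the rule triggers slightly more readily, including at lower true rates: at 20%, the chance of stopping is 18.0% on treated patients, against 12.9% with 1 untreated patient in the denominator and 8.5% with 2.

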8.1 Confidentiality

Information about study subjects will be kept confidential and managed according to the requirements of the Health Insurance Portability and Accountability Act of 1996 (HIPAA). Participants will sign an authorization that includes the following:

- What protected health information (PHI) will be collected from subjects in this study
- Who will have access to that information and why
- Who will use or disclose that information
- The rights of a research subject to revoke their authorization for use of their PHI.

In the event that a subject revokes authorization to collect or use PHI, the investigator, by regulation, retains the ability to use all information collected prior to the revocation of subject authorization.

Loss of patient confidentiality is a risk of participation. Study participant identities will be kept confidential except as required by law. Subjects' samples will be identified by code only (i.e. linked, but de-identified). Patient samples will be de-identified at the time and site of collection. Electronic case report forms, participant, and study information will be kept in the Velos eResearch password protected database. Additionally, documents containing participant identifiers, such as those from the medical record to confirm eligibility, will be filed in binders and kept in a locked, secure location in the Office of Clinical Research at the Norris Cotton Cancer Center.

8.2 Source Documents

Source data are all information, original records of clinical findings, observations, or other activities in a clinical trial necessary for the reconstruction and evaluation of the trial. Source data are contained in source documents. Examples of these original documents, and data records include: hospital records, clinical and office charts, laboratory notes, memoranda, subjects' diaries or evaluation checklists, pharmacy dispensing records, recorded data from automated instruments, copies or transcriptions certified after verification as being accurate and complete, microfiches, photographic negatives, microfilm or magnetic media, x-rays, subject files, and records kept at the pharmacy, at the laboratories, and at medico-technical departments involved in the clinical trial.

8.3 Case Report Forms

The study case report form (CRF) is the primary data collection instrument for the study. All data requested on the CRF will be recorded. All missing data will be explained. If a space on the CRF is left blank because the procedure was not done or the question was not asked, "N/D" will be entered. If the item is not applicable to the individual case, "N/A" will be entered. All entries will be printed legibly in black ink. If any entry error has been made, to correct such an error, a single straight line will be drawn through the incorrect entry and the correct data entered above it. All such changes will be initialed and dated.

ERRORS WILL NOT BE ERASED OR WHITED OUT. For clarification of illegible or uncertain entries, a clarification will be printed above the item, then initialed and dated.

8.4 Records Retention

Following closure of the study, the investigator will maintain all site study records in a safe and secure location. The records are maintained to allow easy and timely retrieval, when needed (e.g., audit or inspection) and, whenever feasible, to allow any subsequent review of data in conjunction with assessment of the facility, supporting systems, and staff. Upon completion of study analysis, research information is stored in Dartmouth College Records Management off-site storage. Documents are shredded on site after 50 years of storage.

Electronic case report forms, participant, and study information will be kept in the Velos eResearch password protected database indefinitely.

9 Study Monitoring, Auditing, and Inspecting

9.1 Safety and Data Monitoring

This study will be monitored by the Data Safety Monitoring and Accrual Committee (DSMAC) of the Norris Cotton Cancer Center. The Committee meets quarterly to review accrual rates and information of all studies that have accrued participants. The DSMAC has the authority to suspend or terminate all research activities that fall within its jurisdiction. In the event that a study is suspended or terminated by the DSMAC, that information will be forwarded to the D-HH IRB.

9.2 On-Site Monitoring

Clinical research monitoring will be conducted by appropriately trained staff of Dartmouth-Hitchcock Medical Center Clinical Trials Office or those of the OCR. This monitoring will include periodic assessment of the regulatory compliance, data quality, pharmacy records, and study integrity. Study records will be reviewed and directly compared to source documents and the conduct of the study will be discussed with the investigator. Monitors may request access to all regulatory documents, source documents, CRFs, and other study documentation for on-site inspection. Direct access to these documents is guaranteed by the investigator, who must provide support at all times for these activities.

9.3 Auditing and Inspecting

Participation as an investigator in this study implies acceptance of potential inspection by government regulatory authorities and applicable Dartmouth Research compliance and quality assurance offices (The Dartmouth CTO). The investigator will permit study-related audits and inspections by the D-HH IRB, government regulatory bodies, and the Dartmouth compliance and quality assurance groups (CTO) of all study related documents (e.g. source documents, regulatory documents, data collection instruments, study data etc.) The investigator will ensure the capability for inspections of applicable study-related facilities (e.g. pharmacy, diagnostic laboratory, etc.).

10 Ethical Considerations

This study is to be conducted according to US and international standards of Good Clinical Practice (FDA Title 21 part 312 and International Conference on Harmonization guidelines), applicable government regulations and Institutional research policies and procedures.

This protocol and any amendments will be submitted, reviewed and approved by the Dartmouth-Hitchcock Health (D-HH) IRB prior to conduct of the study or amendment. All subjects for this study will be provided an IRB-approved consent form describing this study and providing sufficient information for subjects to make an informed decision about their participation in this study. The consent of a subject, using the IRB-approved consent form, must be obtained before that subject undergoes any study procedure. The consent form must be signed by the subject and the investigator-designated research professional obtaining the consent.

11 Study Finances

11.1 Funding Source

This study is funded by the Norris Cotton Cancer Center Clinical Translational Research effort.

14.1 Table summarizing study procedures/flowchart

Visit sequence	Type	Description	Data/Activities
#1	Initial consultation visit	Consults with radiation oncology and neurosurgery	H+P** Protocol screening (check inclusion/exclusion criteria, including pathology/radiology) Protocol consent Bloodwork (CBC, CMP, pregnancy test if indicated) Optional biomarker blood draw Chest imaging if indicated (per section 3.1)
#2	Pre-treatment visit	HBO and SRS preparation	Patient familiarized with HBO technique ("dry run" through the HBO chamber) RT-planning brain MRI VisionRT open face mask fitting CT-based simulation for SRS planning
#3	SRS treatment visit	HBO and SRS treatments	HBO SRS to brain metastases (beam-on goal within 15 minutes after leaving HBO decompression)
#4+	Follow-up visit	Follow-up visits – the first 4-6 weeks after SRS, then every 3 months for two years, then every 4 months for one year, then every 6 months for two years, then annually. Individuals in the substudy for biomarkers will have an additional follow-up the day after the SRS treatment visit.	H+P** Brain MRI Bloodwork at first follow-up visit (CBC, CMP) Optional biomarker blood draw

** Note: All history/physical exam evaluations will include vital signs, performance status, neurological exam, mini-mental status exam, and QOL assessments (EORTC Quality of Life C-30 and BCM20).

14.2 SAE Reporting Form

Please see SAE Reporting Form as detailed on the DHMC CPHS website: <http://www.dartmouth.edu/~cphs/tosubmit/forms/>.

14.3 HBO Treatment Protocol (including “dry run”)

HBO Protocol

14.3.1

Prior to the first visit, any contraindications to hyperbaric treatment will be reviewed. Patients will be scheduled for a chest X-ray, if indicated.

14.3.2

During the first visit patients will have a hyperbaric focused history and physical, and the results of any imaging tests will be reviewed.

Patients will then have a familiarization dive in the chamber. Prior to entering the chamber the patients will have an otoscopic exam. Patients will be placed in the chamber, and the chamber will be pressurized with air to 2.4 ATA. The pressure will then be released. After the patients come out of the chamber they will then have another otoscopic exam.

Patients who have difficulty with equalizing the pressure within their ears will be offered pressure-equalization tubes.

14.3.3

On the treatment day, patients will come first to radiation oncology, where the procedure for the day will be reviewed. The patient will then return to hyperbarics to begin the hyperbaric treatment.

The patients will remove jewelry, watches and any other items that are not approved for use in the chamber (e.g. electronics, matches, lighters, metal objects, cigarettes, car keys, coins/money, batteries, watches, shoes, hand warmers, newspapers, books, magazines, loose medications, stockings, hearing aids). They will remove their street clothes and put on 100% cotton gowns provided by the hyperbaric center.

The chamber will be pressurized to 2.4 ATA at a compression rate (breathing oxygen) of approximately 1 – 3 psi per minute, depending on patient tolerance. The patient will receive hyperbaric oxygen for 30 minutes starting at the time the chamber reaches 2.4 ATA. The decompression rate will be approximately 2-3 psig/fsw per minute depending on patient tolerance. When the treatment is finished, the patient will be removed from the

chamber and transported to the radiation oncology suite via stretcher while receiving 100% non-rebreather face mask @ 15L/min to help maintain oxygen saturation.

The patient will have the Gill-Thomas-Cosman head frame or the VisionRT open face mask placed. Pre-treatment imaging studies then will be performed on the radiation therapy treatment unit, to assure accurate localization of the planned treatment. Stereotactic radiosurgery treatment may then proceed.

The goal for time from leaving the hyperbaric chamber to “beam-on” in the radiation oncology suite is anticipated to be \leq 15 minutes.

